### 4) Information to patients during trial

All written information prepared by Novo Nordisk to patients must be sent to IRB/IEC for approval/favourable opinion and to regulatory authorities for approval or notification according to local regulations. The patient may receive, for example, a "thank you for your participation in this trial" letter.

### 5) Data protection

Patients will be assigned a 6-digit unique identifier, a patient number. Any patient records or datasets that are transferred to Novo Nordisk will contain the identifier only; patient names or any information which would make the patient identifiable will not be transferred.

Protocol  
NN7088-4410

~~CONFIDENTIAL~~

Date: 18 June 2019  
Version: 2.0  
Status: Final  
Page: 70 of 86

**Novo Nordisk**

The patient and any biological material obtained from the patient will be identified by patient number, visit number and trial ID. Appropriate measures such as encryption or leaving out certain identifiers will be enforced to protect the identity of patients as required by local, regional and national requirements.

The patient must be informed that his personal trial related data will be used by Novo Nordisk in accordance with local data protection law. The disclosure of the data must also be explained to the patient.

The patient must be informed that his medical records may be examined by auditors or other authorised personnel appointed by Novo Nordisk, by appropriate IRB/IEC members, and by inspectors from regulatory authorities.

## **6) Committee structure**

### **Novo Nordisk safety committee**

Novo Nordisk has constituted an internal N8-GP safety committee to perform on-going safety surveillance.

The Safety Committee works according to a written guideline. The Safety Committee is responsible for reviewing any safety concern, signal or alert and determining actions to be taken according to the guidelines for the Safety Committee.

### **Data monitoring committee**

As this is an open label and non-randomised trial no data monitoring committee will be established for this trial. An internal Novo Nordisk Safety Committee has been established with the overall responsibility of overseeing the safety of the patients enrolled in the trial.

## **7) Publication policy**

The information obtained during the conduct of this trial is considered confidential, and may be used by or on behalf of Novo Nordisk for regulatory purposes as well as for the general development of the trial product. All information supplied by Novo Nordisk in connection with this trial shall remain the sole property of Novo Nordisk and is to be considered confidential information.

No confidential information shall be disclosed to others without prior written consent from Novo Nordisk. Such information shall not be used except in the performance of this trial.

The information obtained during this trial may be made available to other investigators who are conducting other clinical trials with the trial product, if deemed necessary by Novo Nordisk. Provided that certain conditions are fulfilled, Novo Nordisk may grant access to information

Protocol  
NN7088-4410

~~CONFIDENTIAL~~

Date:  
Version:  
Status:  
Page:

18 June 2019  
2.0  
Final  
71 of 86

**Novo Nordisk**

obtained during this trial to researchers who require access for research projects studying the same disease and/or trial product studied in this trial.

Novo Nordisk may publish on its clinical trials website a redacted clinical trial report for this trial. One investigator will be appointed by Novo Nordisk to review and sign the clinical trial report (signatory investigator) on behalf of all participating investigators.

### **Communication of results**

Novo Nordisk commits to communicate and disclose results of trials regardless of outcome. Disclosure includes publication of a manuscript in a peer-reviewed scientific journal, abstract submission with a poster or oral presentation at a scientific meeting or disclosure by other means.

The results of this trial will be subject to public disclosure on external web sites according to international and national regulations. Novo Nordisk reserves the right to defer the release of data until specified milestones are reached, for example when the clinical trial report is available. This includes the right not to release the results of interim analyses, because the release of such information may influence the results of the entire trial.

At the end of the trial, one or more scientific publications may be prepared collaboratively by the investigator(s) and Novo Nordisk. Novo Nordisk reserves the right to postpone publication and/or communication for up to 60 days to protect intellectual property.

In all cases the trial results will be reported in an objective, accurate, balanced and complete manner, with a discussion of the strengths and limitations. In the event of any disagreement on the content of any publication, both the investigators' and Novo Nordisk opinions will be fairly and sufficiently represented in the publication.

### **Authorship**

Novo Nordisk will work with one or more investigator(s) and other experts who have contributed to the trial concept or design, acquisition, analysis or interpretation of data to report the results in one or more publications.

Authorship of publications should be in accordance with the Recommendations for the Conduct, Reporting, Editing and Publication of Scholarly Work in Medical Journals by the International Committee of Medical Journal Editors .

All authors will be provided with the relevant statistical tables, figures, and reports needed to evaluate the planned publication.

Where required by the journal, the investigator from each trial site will be named in an acknowledgement or in the supplementary material, as specified by the journal.

Protocol  
NN7088-4410

~~CONFIDENTIAL~~

Date:  
Version:  
Status:  
Page:

18 June 2019  
2.0  
Final  
72 of 86

**Novo Nordisk**

### **Site-specific publication(s) by investigator(s)**

For a multicentre clinical trial, analyses based on single-site data usually have significant statistical limitations and frequently do not provide meaningful information for healthcare professionals or patients, and therefore may not be supported by Novo Nordisk. Thus, Novo Nordisk may deny a request or ask for deferment of the publication of individual site results until the primary manuscript is accepted for publication. In line with Good Publication Practice, such individual reports should not precede the primary manuscript and should always reference the primary manuscript of the trial.

### **Investigator access to data and review of results**

As owner of the trial database, Novo Nordisk has the discretion to determine who will have access to the database.

Individual investigators will have their own research patients' data.

### **8) Dissemination of clinical trial data**

Information of the trial will be disclosed at [clinicaltrials.gov](http://clinicaltrials.gov) and [novonordisk-trials.com](http://novonordisk-trials.com). It will also be disclosed according to other applicable requirements such as those of the International Committee of Medical Journal Editors (ICMJE), the Food and Drug Administration Amendment Act (FDAAA), European Commission Requirements and other relevant recommendations or regulations. If a patient requests to be included in the trial via the Novo Nordisk e-mail contact at these web sites, Novo Nordisk may disclose the investigator's contact details to the patient. As a result of increasing requirements for transparency, some countries require public disclosure of investigator names and their affiliations.

The Primary Completion Date (PCD) is the last assessment of the primary endpoint, and is for this trial corresponding to visit EoT. If the last patient is withdrawn early, the PCD is considered the date when the last patient would have completed visit EoT. The PCD determines the deadline for results disclosure at [clinicaltrials.gov](http://clinicaltrials.gov) according to FDAAA.

### **9) Data quality assurance**

#### **Case Report Forms (CRFs)**

Novo Nordisk or designee is responsible for the data management of this trial including quality checking of the data.

All patient data relating to the trial will be recorded on eCRFs and paper CRFs unless transmitted electronically to Novo Nordisk or designee (e.g. laboratory data). The investigator is responsible for verifying that data entries are accurate and correct by physically or electronically signing the eCRF.

Novo Nordisk will provide a system for the eCRFs. This system and support services to the system will be provided by an external supplier. The activities of this vendor will be under the direction and supervision of Novo Nordisk.

Protocol  
NN7088-4410

~~CONFIDENTIAL~~

Date:  
Version:  
Status:  
Page:

18 June 2019  
2.0  
Final  
73 of 86

**Novo Nordisk**

The investigator or delegated person has to ensure that all relevant questions are answered, and that no empty data field exists. If a test or an assessment has not been done and will not be available, or if the question is irrelevant (e.g. is not applicable), indicate this according to the data entry instructions.

The following will be provided as paper CRFs:

- PRO questionnaires
- Paper Diary

The following will be provided as paper CRFs to be used when access to the eCRF is revoked or if the eCRF is unavailable:

- AE forms
- Pregnancy forms
- Safety information forms
- Technical complaint forms

On the paper CRF forms print legibly, using a ballpoint pen. Ensure that all questions are answered, and that no empty data blocks exist. Ensure that no information is recorded outside the data blocks. If a test/assessment has not been done and will not be available, indicate this by writing “ND” (not done) in the appropriate answer field in the CRF. If the question is irrelevant (e.g. is not applicable) indicate this by writing “NA” (not applicable) in the appropriate answer field. Further guidance can be obtained from the instructions in the CRF.

The investigator must ensure that all information is consistent with the source documentation. By electronically signing the case book in the eCRF, the investigator confirms that the information in the eCRF and related forms is complete and correct.

#### **Corrections to eCRFs**

Corrections to the eCRF data may be made by the investigator or the investigator’s delegated staff. An audit trail will be maintained in the eCRF application containing as a minimum: the old and the new data, identification of the person entering the data, date and time of the entry and reason for the correction.

If corrections are made by the investigator’s delegated staff after the date when the investigator signed the eCRF, the eCRF must be signed and dated again by the investigator.

#### **Corrections in paper CRFs**

The investigator must ensure that data is recorded in the CRF as soon as possible after the visit. If corrections are made by the investigator’s delegated staff after the date of the investigator’s signature on the affirmation statement, the affirmation statement must be signed and dated again by the investigator.

Protocol  
NN7088-4410

~~CONFIDENTIAL~~

Date:  
Version:  
Status:  
Page:

18 June 2019  
2.0  
Final  
74 of 86

**Novo Nordisk**

Corrections necessary after the CRFs have been removed from the trial site must be documented on a Data Clarification Form (DCF) or a Monitor Initiated Discrepancy Form (MIDF). If the affirmation statement for the patient has not yet been signed, any corrections must be approved by the investigator or her/his delegated staff. If the affirmation statement for the patient has already been signed, the investigator must approve any correction.

If a CRF accountability page is not implemented, then an alternative CRF accountability system should be set up ensuring a central and easy overview of unused or missing pages at patient level.

### **Case report form flow**

The investigator must ensure that data is recorded in the CRF as soon as possible, preferably within 5 working days after the visit. Once data has been entered, it will be available to Novo Nordisk for data verification and validation purposes. Queries to data in the eCRF must be answered in the system preferably within 3 days and during interim or DBL preferably daily.

When the final clinical trial report (CTR) is available, the data will be archived by Novo Nordisk.

### **Paper Diary**

Novo Nordisk will provide the patient and/or LAR with a paper diary for recording of details of their home treatment, bleeding episodes and treatment of bleeding episodes.

Patients will be instructed in the use of the diary by the investigator or delegated person before recording any data.

The diaries will be returned by the patient at every visit.

### **Investigator review of Diary data**

It is the responsibility of the Investigator or delegated staff to review and enter the diary data reported by the patient. As a minimum it must be verified that the diary data is complete, consistent and according to the requirements defined in this protocol. This also includes the number of doses reported in the diary reviewed against the number of vials accounted for actually used by the patient.

Upon review the Investigator or delegated staff must document that the review has taken place and any actions required e.g. retraining of the patient and/or change to the data. Changes can only be done if the patient confirms the correctness of the data.

### **Monitoring**

The investigator must permit trial-related monitoring, audits, IRB/IEC review, and regulatory agency inspections and provide direct access to source data documents (original documents, data and records). Direct access includes permission to examine, analyse, verify and reproduce any record(s) and report(s) that are important to the evaluation of the trial. If the electronic medical

Protocol  
NN7088-4410

~~CONFIDENTIAL~~

Date: 18 June 2019  
Version: 2.0  
Status: Final  
Page: 75 of 86

**Novo Nordisk**

record does not have a visible audit trail, the investigator must provide the monitor with signed and dated printouts. In addition the relevant trial site staff should be available for discussions at monitoring visits and between monitoring visits (e.g. by telephone).

Trial monitors will perform on-going source data verification to confirm that data entered into the eCRF by authorised site personnel are accurate, complete and verifiable from source documents; that the safety and rights of patients are being protected, to monitor drug accountability and collect completed paper CRF pages, if applicable, and that the trial is being conducted in accordance with the currently approved protocol and any other trial agreements, ICH GCP, and all applicable regulatory requirements.

Monitoring will be conducted using a risk based approach including risk assessment, monitoring plans, centralised monitoring (remote assessment of data by Novo Nordisk) and visits to trial sites.

Monitors will review the patient's medical records and other source data e.g. the diaries and PROs, to ensure consistency and/or identify omissions compared to the eCRF.

### **Protocol compliance**

Deviations from the protocol should be avoided. If deviations do occur, the investigator must inform the monitor and the implications of the deviation must be reviewed and discussed.

Deviations must be documented and explained in a protocol deviation by stating the reason, date, and the action(s) taken. Some deviations, for which corrections are not possible, can be acknowledged and confirmed via edit checks in the eCRF or via listings from the trial database.

### **10) Source documents**

All data entered in the eCRF must be verifiable in source documentation other than the eCRF.

The original of the completed diaries and PROs must not be removed from the trial site.

Source documents provide evidence for the existence of the patient and substantiate the integrity of the data collected. Source documents are filed at the trial site.

Data reported on the paper CRF or entered in the eCRF that are transcribed from source documents must be consistent with the source documents or the discrepancies must be explained. The investigator may need to request previous medical records or transfer records. Also, current medical records must be available.

It must be possible to verify patient's medical history in source documents such as patient's medical record. Haemophilia details will be obtained from the baseline data recorded on the patient in previous trial (NN7088-3859 (pathfinder2) or NN7088-3885 (pathfinder5))

Protocol  
NN7088-4410

~~CONFIDENTIAL~~

Date:  
Version:  
Status:  
Page:

18 June 2019  
2.0  
Final  
76 of 86

**Novo Nordisk**

The investigator must document any attempt to obtain external medical information by noting the date(s) when information was requested and who was contacted.

Definition of what constitutes source data can be found in a source document agreement at each trial site. There will only be one source document defined at any time for any data element.

### **11) Retention of clinical trial documentation**

Records and documents, including signed informed consent forms, pertaining to the conduct of this trial must be retained by the investigator for 15 years after end of trial unless local regulations or institutional policies require a longer retention period. No records may be destroyed during the retention period without the written approval of Novo Nordisk. No records may be transferred to another location or party without written notification to Novo Nordisk.

The investigator must be able to access his/her trial documents without involving Novo Nordisk in any way. If applicable, eCRF and other patient data will be provided in an electronic readable format to the investigator before access is revoked to the systems supplied by Novo Nordisk. Site-specific eCRFs and other patient data (in an electronic readable format or as paper copies or prints) must be retained by the trial site. If the provided electronic data (e.g. the CD-ROM) is not readable during the entire storage period, the investigator can request a new copy. A copy of all data will be stored by Novo Nordisk.

Patient's medical records must be kept for the maximum period permitted by the hospital, institution or private practice

### **12) Trial and site closure**

Novo Nordisk reserves the right to close the trial site or terminate the trial at any time for any reason at the sole discretion of Novo Nordisk. If the trial is suspended or terminated, the investigator must inform the patients promptly and ensure appropriate therapy and follow-up. The investigator and/or Novo Nordisk must also promptly inform the regulatory authorities and IRBs/IECs and provide a detailed written explanation.

Trial sites will be closed upon trial completion. A trial site is considered closed when all required documents and trial supplies have been collected and a trial site closure visit has been performed.

The investigator may initiate trial site closure at any time, provided there is reasonable cause and sufficient notice is given in advance of the intended termination.

Reasons for the early closure of a trial site by Novo Nordisk or investigator may include but are not limited to:

- failure of the investigator to comply with the protocol, the requirements of the IRB/IEC or local health authorities, Novo Nordisk procedures or GCP guidelines
- inadequate recruitment of patients by the investigator

- discontinuation of further trial product development.

### **13) Responsibilities**

The investigator is accountable for the conduct of the trial at his/her site and must ensure adequate supervision of the conduct of the trial at the trial site. If any tasks are delegated, the investigator must maintain a log of appropriately qualified persons to whom he/she has delegated specified trial-related duties. The investigator must ensure that there is adequate and documented training for all staff participating in the conduct of the trial. It is the investigator's responsibility to supervise the conduct of the trial and to protect the rights, safety, and well-being of the patients.

A qualified physician, who is an investigator or a sub-investigator for the trial, must be responsible for all trial-related medical decisions.

The investigator is responsible for filing essential documents (i.e. those documents which individually and collectively permit evaluation of the conduct of a trial and the quality of the data produced) in the investigator trial master file. The documents, including the patient identification code list must be kept in a secure locked facility so that no unauthorized persons can get access to the data.

The investigator will take all necessary technical and organisational safety measures to prevent accidental or wrongful destruction, loss or deterioration of data. The investigator will prevent any unauthorised access to data or any other processing of data against applicable law. The investigator must be able to provide the necessary information or otherwise demonstrate to Novo Nordisk that such technical and organisational safety measures have been taken.

During any period of unavailability, the investigator must delegate responsibility for medical care of patients to a specific qualified physician who will be readily available to patients during that time.

If the investigator is no longer able to fulfil the role as investigator (e.g. if he/she moves or retires) a new investigator will be appointed in consultation with Novo Nordisk.

The investigator and other site personnel must have sufficient English skills according to their assigned task(s).

### **14) Indemnity statement**

Novo Nordisk carries product liability for its products, and liability as assumed under the special laws, acts and/or guidelines for conducting clinical trials in any country, unless others have shown negligence.

Protocol  
NN7088-4410

~~CONFIDENTIAL~~

Date:	18 June 2019
Version:	2.0
Status:	Final
Page:	78 of 86

**Novo Nordisk**

Novo Nordisk assumes no liability in the event of negligence or any other liability of the sites or investigators conducting the trial or by persons for whom the said site or investigator are responsible.

Novo Nordisk accepts liability in accordance with local laws and guidelines, see [Appendix 8](#).

### **15) Web-portal for document exchange**

During the trial a web-portal will be used for document exchange between Novo Nordisk and the sites. The web-portal is not an archiving tool but could be used as a temporary archiving place during the trial as judged by the investigator.

Protocol  
 NN7088-4410

~~CONFIDENTIAL~~

Date: 18 June 2019  
 Version: 2.0  
 Status: Final  
 Page: 79 of 86

**Novo Nordisk**

## Appendix 4 Adverse events: definitions and procedures for recording, evaluation, follow-up, and reporting

AE definition
 
 
• An AE is any untoward medical occurrence in a clinical trial patient that is temporally associated with the use of a medicinal product, whether or not considered related to the medicinal product.
 
• An AE can be any unfavourable and unintended sign, including an abnormal laboratory finding, symptom or disease (new or exacerbated) temporally associated with the use of a medicinal product.
 

--

Events meeting the AE definition
 
 
• Any abnormal laboratory test results or safety assessments, including those that worsen from baseline, considered clinically significant in the medical and scientific judgment of the investigator.
 
• A CLAE: a clinical abnormal laboratory finding which is clinically significant, i.e. an abnormality that suggests a disease and/or organ toxicity and is of a severity that requires active management. Active management includes active treatment or further investigations, for example change of medicine dose or more frequent follow-up due to the abnormality.
 
• Exacerbation of a chronic or intermittent pre-existing condition including either an increase in frequency and/or intensity of the condition.
 
• Signs, symptoms or the clinical sequelae of a suspected drug-drug interaction.
 
• Signs, symptoms or the clinical sequelae of a suspected overdose of trial product regardless of intent..
 

--

Events NOT meeting the AE definition
 
 
• Pre-existing conditions, anticipated day-to-day fluctuations of pre-existing conditions, including those identified during screening or other trial procedures performed before exposure to trial product.
 
 
Note: pre-existing conditions other than haemophilia should be recorded as medical history/concomitant illness.
 
 
• Pre-planned procedures, unless the condition for which the procedure was planned has worsened from the first trial related activity after the patient has signed the informed consent.
 

--


Definition of an SAE
 
An SAE is an AE that fulfils at least one of the following criteria:
 
 
• Results in death
 
• Is life-threatening
 
 
The term 'life-threatening' in the definition of 'serious' refers to an event in which the patient was at risk of death at the time of the event. It does not refer to an event which hypothetically might have caused death, if it were more severe.
 
 
• Requires inpatient hospitalisation or prolongation of existing hospitalisation
 
 
 
• Hospitalisation signifies that the patient has been detained at the hospital or emergency ward for observation and/or treatment that would not have been appropriate in the physician's office or outpatient setting. Complications that occur during hospitalisation are AEs. If a complication prolongs hospitalisation or fulfils any other serious criteria, the event is serious. When in doubt as to whether "hospitalisation" occurred or was necessary, the AE should be considered serious.
 
• Hospitalisation for elective treatment of a pre-existing condition that did not worsen from baseline is not considered an AE.
 
 
Note:
 
 
▪ Hospitalisations for administrative, trial related and social purposes do not constitute AEs and should therefore not be reported as AEs or SAEs.
 
▪ Hospital admissions for surgical procedures, planned before trial inclusion, are not considered AEs or SAEs.
 
 
 
• Results in persistent disability/incapacity
 

--

Protocol  
 NN7088-4410

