#### 9.4 Patient related info/assessments

**Demography** consists of date of birth and age (unless not allowed according to local regulation, see [Appendix 8](#)), ethnicity and race (unless not allowed according to local regulation, see [Appendix 8](#))

A **concomitant illness** is any illness other than haemophilia that is present at the start of the trial (i.e. at the first visit) or found as a result of a screening procedure or other trial procedures performed before exposure to trial product.

**Medical history** is a medical event other than haemophilia that the patient has experienced in the past. This will include joint status at screening:

- List of joints which during the patient’s life have caused special problems, in terms of repeated or frequent bleeding episodes. This list can be compiled through discussion between the patient/parent(s) and investigator
- List of joints with arthropathy

In case of an abnormal and clinically significant finding other than haemophilia, the investigator must record the finding on the Medical History/Concomitant Illness form if it is present at screening. Any new finding fulfilling the AE definition (see [Appendix 4](#)) during the trial and any clinically significant worsening from baseline (Screening/V1) must be reported as an AE (see Section [9.6](#)).

**Details of haemophilia / haemophilia treatment and bleed history** is any data from the previous trial NN7088-3859 (pathfinder2) or NN7088-3885 (pathfinder5) in relation to previous regimens and bleeding episodes.

**Genotype testing** during trials NN7088-3859 (pathfinder2) and NN7088-3885 (pathfinder5) was offered to all patients unless not allowed according to local regulation.

**AB0 blood group** will be collected in eCRF as A, B, AB, 0 or not assessed based on medical records

**Concomitant medication** is any medication, other than the trial product, that is taken during the trial

Available demography, details of haemophilia treatment and bleeding episodes, and genotype will be transferred from previous trial NN7088-3859 (pathfinder2) or NN7088-3885 (pathfinder5).

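### The Note on surgical admissions in Appendix 4 lacks the worsening exception that two neighbouring rules carry, so SAE status and 24-hour reporting can be decided differently for the same event

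*Protocol*

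**What the plan says.** Three rules in Protocol Appendix 4 bear on a patient who enters the trial with an operation already planned.

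- **Events not meeting the AE definition.** The list includes "Pre-planned procedures, unless the condition for which the procedure was planned has worsened from the first trial related activity" (counted from after consent). The exclusion therefore stops once the condition has worsened.
- **Definition of an SAE, hospitalisation criterion.** "Hospitalisation for elective treatment of a pre-existing condition that did not worsen from baseline is not considered an AE". This exclusion is also confined to a condition that has not worsened.
- **Definition of an SAE, Note under the same criterion.** "Hospital admissions for surgical procedures, planned before trial inclusion, are not considered AEs or SAEs". No exception for worsening is given.

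The seriousness criterion to which the last two rules belong is "Requires inpatient hospitalisation or prolongation of existing hospitalisation".

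SAEs are summarised and listed alongside all AEs under the primary endpoint (Protocol 10.3.1, repeated in SAP 2.3.1). They must be reported to the sponsor within 24 hours (Protocol 9.6.1).

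**The concern.** The first two rules keep an event reportable when the condition deteriorates on trial. Read literally, the Note takes the admission out of both AE and SAE reporting whatever happened to the condition. The worsening limit is written twice and missing the third time, which looks like a drafting slip rather than a policy. Even so, the Note is the most specific text on surgical admissions and sits where a site looks when deciding on seriousness, so a site could reasonably follow it.

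The situation is plausible in this trial. All patients come from earlier trials of the same product. Minor and major surgery are allowed (Protocol 7.1.4), major elective orthopaedic surgery is part of the major-surgery definition, and joints with arthropathy are listed at screening (Protocol 9.4). A joint already awaiting an operation may deteriorate after entry.

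At stake are the consistency of the SAE table and the 24-hour report. Two sites could classify the same event differently, each relying on Appendix 4.

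**Working it through.** No arithmetic decides this point, so the check applies the rules case by case. In every case the operation was planned before inclusion.

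1. **Condition unchanged, surgery as planned.** All three rules agree: neither AE nor SAE.
2. **Condition worsened, surgery goes ahead or is brought forward, no other seriousness criterion met.** The first two rules no longer exclude the event. The worsening is an AE, and the hospitalisation criterion is then open. The Note still excludes the admission. The rules conflict.
3. **Condition worsened and caused an unplanned or emergency admission.** That admission was arguably not planned before inclusion, so the Note does not reach it and the hospitalisation criterion applies.
4. **Condition worsened and met another criterion** (death, threat to life, disability, important medical event). It is an SAE whatever the Note says.
5. **Complication during the planned stay.** Appendix 4 makes it an AE, and serious if it prolongs the stay or meets another criterion.

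Only case 2 is affected.

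**Is the worsening still recorded as an AE in case 2?** Yes, in general, by rules the Note does not touch:

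- Appendix 4 lists as meeting the AE definition "Exacerbation of a chronic or intermittent pre-existing condition including either an increase in frequency and/or intensity of the condition".
- Protocol 9.4 says that "any clinically significant worsening from baseline (Screening/V1) must be reported as an AE".
- Protocol 9.5.2 has clinically significant joint findings that arise during the trial recorded as AEs.

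**Does any text settle case 2?** The tie-break in Appendix 4 resolves doubt about whether hospitalisation occurred or was necessary. It does not say whether an admission planned in advance counts. The SAP adds nothing on it.

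**Reference time points.** The first rule measures worsening from the first trial-related activity after consent. The second measures it from baseline, which Protocol 9.4 equates with Screening/V1. The Note mentions only trial inclusion, and uses it to date the planning of the surgery rather than any worsening.

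**Size.** The number of affected events is the number of patients with surgery planned before inclusion whose condition then worsened on trial and who fall into case 2. The documents give none of these counts, so no figure can be derived.

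**The case against.** The strongest defence is that the Note speaks of the admission, not of the worsened condition. An SAE is an AE that requires hospitalisation, and an admission already in the diary before entry was not required by something that happened later. On that view the Note only spares sites from reporting scheduled admissions, and the bullet just above it preserves the worsening limit.

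Much of this stands. It is a coherent reading for surgery that takes place on its planned date, and it shows that the worsening itself is not erased. It does not deal with surgery brought forward because of the worsening. It is also an inference that the text does not state, and the Note's wording reaches further than it does.

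The affected group is narrowed again by Protocol Table 9-5: symptoms caused by the underlying disease in connection with bleeding episodes are not reported as AEs at all. Part of what might look like joint deterioration in haemophilia therefore falls outside AE reporting for a different reason.

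A reader might draw two stronger inferences. Neither is supported.

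- **That the event disappears altogether and the primary endpoint is under-counted.** The exacerbation rule and Protocol 9.4 and 9.5.2 still require the worsening to be recorded as an AE.
- **That the sample-size statement is undermined.** Protocol 10.1 gives a 95% upper bound of 0.02 for an adverse event not observed among at least 150 patients. That figure reproduces: 1 − 0.05^(1/150) = 0.0198, and 3/150 = 0.02. It concerns whether an event of a given type occurred, not whether it was serious. Because the AE is still recorded, the Note does not turn an observed event into an unobserved one, and the bound is unaffected.

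**Conclusion.** Appendix 4 is internally inconsistent, and the inconsistency is in the current protocol text. Its effect is limited to SAE classification and 24-hour reporting. It arises only where admission for a pre-planned operation, carried out on schedule or brought forward after an on-trial worsening, is the sole seriousness criterion. The primary AE count need not change.

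The conclusion assumes that sites apply the other AE rules as written and record the worsening. How often the case arises cannot be established from the documents. Severity is minor: the contradiction in wording is clear, but its consequence is narrow.

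**What to change.** Reconcile the three rules in Appendix 4.

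- Add to the Note the exception that the other two rules already carry: unless the condition has worsened since the first trial-related activity after informed consent.
- Use that same reference time point in all three rules.
- State that such a worsening is reported as an AE, and as an SAE if it meets a seriousness criterion.

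The cost is one clause in the Note plus harmonised wording in the two neighbouring rules. No treatment, visit or analysis changes. The only downside is that a few more SAEs may be reported.
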